### 1.2 Intervention(s)

#### 1.2.1 Brief description of the study intervention(s)

**Dose-escalation group (DE-group):** This group consists of 40 persons with Parkinson's disease who will receive an escalating dose of NR over three months: month one NR 1000 mg daily, month two NR 2000 mg daily, month three NR 3000 mg daily.

**Dose-stable group (DS-group):** This group consists of 20 persons with Parkinson's disease who will receive a dose of NR 1000 mg daily for three months.

#### 1.2.2 Control settings (if applicable)

**Placebo (PL-group):** This group consists of 20 persons with Parkinson's disease who will receive placebo for three months.

### 1.3 Trial Objectives

#### 1.3.1 Primary Objective

The primary objective of this study is to compare the effect of orally administered nicotinamide riboside (NR), escalated to 1500 mg twice per day (3000 mg/day) in the dose-escalation group (DE-group) versus stable dosing of 500 mg twice per day (1000 mg/day) in the dose-stable group (DS-group) on cerebral NAD-levels at week 12.

#### 1.3.2 Secondary Objectives

The secondary objectives of this study are to:

- Assess the dose-response relationship between NR dose (1000 mg, 2000 mg, 3000 mg per day) and changes in cerebral NAD levels from baseline to weeks 4, 8 and 12.

- Compare the effectiveness of orally administered nicotinamide riboside (NR) 1500 mg twice per day versus 500 mg twice per day in augmenting the NAD-metabolome in the central nervous system (CNS) at week 12.

### 1.3.3 Exploratory Objectives

The exploratory objectives of this study are:

- To compare the effect of orally administered NR in the DE-group versus DS-group on the NR related metabolic pattern (NRRP) expression at week 12.
- To assess the dose-response relationship between NR dose (1000 mg, 2000 mg, 3000 mg per day) and changes in NRRP expression from baseline to weeks 4, 8 and 12.
- To compare the effect of orally administered NR DE-group versus DS-group on the PD-related pattern (PDRP) expression at week 12.
- To assess the dose-response relationship between NR dose (1000 mg, 2000 mg, 3000 mg per day) and changes in PDRP expression from baseline to weeks 4, 8 and 12.
- To compare the effect of orally administered NR in the DE-group versus DS-group on the NAD metabolome\* in the blood, urine and central nervous system (CNS) at week 12.
- To assess the dose-response relationship between NR dose (1000 mg, 2000 mg, 3000 mg per day) and changes in the NAD metabolome\* in blood and urine from baseline to weeks 4, 8 and 12.
- To compare the effect of orally administered NR in the DE-group versus DS-group on clinical severity of PD symptoms at week 12.
- To assess the dose-response relationship between NR dose (1000 mg, 2000 mg, 3000 mg per day) and change in clinical severity of PD symptoms from baseline to weeks 4, 8 and 12.
- To compare the effect of orally administered NR in the DE-group versus DS-group on severity of non-motor symptoms of daily living in PD at week 12.
- To assess the dose-response relationship between NR dose (1000 mg, 2000 mg, 3000 mg per day) and change in severity of non-motor symptoms of daily living in PD from baseline to weeks 4, 8 and 12.
- To compare the effect of orally administered NR in the DE-group versus DS-group on severity of motor aspects of experiences of daily living in PD at week 12.
- To assess the dose-response relationship between NR dose (1000 mg, 2000 mg, 3000 mg per day) and changes in severity of motor aspects of experiences of daily living in PD from baseline to weeks 4, 8 and 12.
- To compare the effect of orally administered NR in the DE-group versus DS-group on severity of PD motor symptoms at week 12.
- To assess the dose-response relationship between NR dose (1000 mg, 2000 mg, 3000 mg per day) and changes in severity of PD motor symptoms from baseline to weeks 4, 8 and 12.
- To compare the effect of orally administered NR in the DE-group versus DS-group on severity PD motor complications at week 12.
- To assess the dose-response relationship between NR dose (1000 mg, 2000 mg, 3000 mg per day) and changes in severity of PD motor complications from baseline to weeks

- 4, 8 and 12.
- To compare the effect of orally administered NR in the DE-group versus DS-group on clinical severity of PD non-motor symptoms at week 12.
  - To assess the dose-response relationship between NR dose (1000 mg, 2000 mg, 3000 mg per day) and changes in clinical severity of PD non-motor symptoms from baseline to weeks 4, 8 and 12.
  - To compare the effect of orally administered NR in the DE-group versus DS-group on clinical severity of gastrointestinal non-motor dysfunction in PD at week 12.
  - To assess the dose-response relationship between NR dose (1000 mg, 2000 mg, 3000 mg per day) and changes in clinical severity of gastrointestinal non-motor dysfunction in PD from baseline to weeks 4, 8 and 12.
  - To compare the effect of orally administered NR in the DE-group versus DS-group on cognition at week 12.
  - To assess the dose-response relationship between NR dose (1000 mg, 2000 mg, 3000 mg per day) and changes in cognition from baseline to weeks 4, 8 and 12.
  - To compare the effect of orally administered NR in the DE-group versus DS-group on quality of life in PD at week 12.
  - To assess the dose-response relationship between NR dose (1000 mg, 2000 mg, 3000 mg per day) and changes in quality of life in PD from baseline to weeks 4, 8 and 12.
  - To compare the effect of orally administered NR in the DE-group versus DS-group on gene expression at week 12.
  - To assess the dose-response relationship between NR dose (1000 mg, 2000 mg, 3000 mg per day) and changes in gene expression from baseline to weeks 4, 8 and 12.
  - To compare the effect of orally administered NR in the DE-group versus DS-group on protein expression at week 12.
  - To assess the dose-response relationship between NR dose (1000 mg, 2000 mg, 3000 mg per day) and changes in protein expression from baseline to weeks 4, 8 and 12.
  - To compare the effect of orally administered NR in the DE-group versus DS-group on serum and CSF inflammatory markers at week 12.
  - To assess the dose-response relationship between NR dose (1000 mg, 2000 mg, 3000 mg per day) and changes in serum inflammatory markers from baseline to weeks 4, 8 and 12.
  - To compare the effect of orally administered NR in the DE-group versus DS-group on histone acetylation in PD at week 12.
  - To assess the dose-response relationship between NR dose (1000 mg, 2000 mg, 3000 mg per day) and changes in histone acetylation in PD from baseline to weeks 4, 8 and 12.
  - To compare the effect of orally administered NR in the DE-group versus DS-group on H3K27 and H4K16 histone acetylation in PD at week 12.
  - To assess the dose-response relationship between NR dose (1000 mg, 2000 mg, 3000 mg per day) and changes in on H3K27 and H4K16 histone acetylation in PD from baseline to weeks 4, 8 and 12.
  - To compare the effect of orally administered NR in the DE-group versus DS-group on the genomic distribution of H3K27 and H4K16 histone acetylation in PD at week 12.

- To assess the dose-response relationship between NR dose (1000 mg, 2000 mg, 3000 mg per day) and changes in the genomic distribution of H3K27 and H4K16 histone acetylation in PD from baseline to weeks 4, 8 and 12.
- To compare the effect of orally administered NR in the DE-group versus DS-group on folate and one-carbon metabolism in PD at week 12.
- To assess the dose-response relationship between NR dose (1000 mg, 2000 mg, 3000 mg per day) and changes in folate and one-carbon metabolism in PD from baseline to weeks 4, 8 and 12.
- To compare the effect of orally administered NR in the DE-group versus DS-group on methyl donors in PD at week 12.
- To assess the dose-response relationship between NR dose (1000 mg, 2000 mg, 3000 mg per day) and changes in methyl-donors in PD from baseline to weeks 4, 8 and 12.
- To compare the effect of orally administered NR in the DE-group versus DS-group on DNA methylation at week 12.
- To assess the dose-response relationship between NR dose (1000 mg, 2000 mg, 3000 mg per day) and changes in methyl-donors in PD from baseline to weeks 4, 8 and 12.
- To compare the effect of orally administered NR in the DE-group versus DS-group on synthesis of neurotransmitters in PD at week 12.
- Determine whether NR-therapy affects the gut microbiome in a dose-responsive manner at week 12.
- To compare the effect of orally administered NR in the DE-group versus DS-group on the gut metabolome at week 12.
- To compare the effect of orally administered NR in the DE-group versus DS-group on the sense of smell at week 12.
- To determine the safety and tolerability of NR at a dose of 1000 mg, 2000 mg, and 3000 mg per day in PD.

**\*The NAD metabolome is comprised of:** Nicotinamide adenine dinucleotide oxidized (NAD+), Nicotinamide adenine dinucleotide reduced (NADH), NAD+/NADH ratio, total NAD (sum of NAD+ and NADH), Nicotinamide adenine dinucleotide phosphate oxidized (NADP+), Nicotinamide adenine dinucleotide phosphate reduced (NADPH), NADP+/NADPH ratio, total NADP (sum of NADP+ and NADPH), 1-methyl nicotinamide (Me-Nam), nicotinic acid-adenine dinucleotide (NAAD), N1-methyl-2-pyridone-5-carboxamide (Me-2-PY), Nicotinamide (Nam), Nicotinamide N-oxide (Nam N-oxide), ADP-ribose (ADPR), Nicotinic acid riboside (NAR), Nicotinamide riboside (NR), Nicotinamide mononucleotide (NMN), Nicotinic acid (NA).

## 2 Trial Methods

### 2.1 Trial Design

The N-DOSE study is designed as a randomized, double blind, placebo-controlled, parallel-group, single-centre, phase II dose-optimization study. Treatment allocation is a 1:1:2 ratio. Patients are randomized to either placebo, dose escalation up to 3000 mg NR or stable dose of 1000 mg NR for three months.

### 2.2 Randomisation

Eligible patients are allocated in a 1:1:2 ratio between placebo, DS and DE groups, using the electronic case report form (eCRF) vieDoc.com (www.viedoc.com, version 4.77.8648.13864).

The randomization process is described in full within the clinical trial protocol. Details of the randomization including the final random allocation list are held securely and unavailable to unauthorized trial personnel.

### 2.3 Statistical Framework

#### 2.3.1 Hypothesis Test

This trial is designed to investigate the dose-responsiveness of NR treatment in a dose escalation group compared to a dose stable group and compared to placebo over three months.

The primary null hypothesis (H0) is that the NR-induced increase in cerebral NAD levels (measured by P-MRS) is not dose-responsive.

The alternative hypothesis (HA) is that NR-induced increase in cerebral NAD levels is dose responsive.

There is only one identified primary analysis in this trial. All other efficacy analyses will be regarded as secondary or exploratory.

#### 2.3.2 Confidence Intervals and p-values

All calculated p-values will be two-sided and compared to a 5% significance level. If a p-value is less than 0.05, the corresponding treatment group difference will be denoted as statistically significant. All efficacy estimates will be presented with two-sided 95% confidence intervals. As there is only one primary null hypothesis to be tested in this trial, there will be no adjustments for multiplicity.

#### 2.3.3 Decision Rule

This trial is designed to address a single primary outcome. Non-inferiority is claimed if the primary null hypothesis is rejected on the significance level (alpha) of 0.025 (one-sided). That is, if the upper limit of the 95% two-sided confidence interval for the treatment difference is less than 15%.

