## 10.4 Planned analyses

All statistical analyses will take place after the completion of the study. All randomized patients will be included in the primary analyses and sensitivity analyses will be carried out comparing results from the ITT, SAS and PPS data sets. In the case of missing assessments, the subject will be included if possible.

The **primary analysis** of the primary endpoint will be performed using analysis of covariance (ANCOVA) between the dose stable (DS-group) and dose escalation group (DS-group), i.e. the regression of NAD levels measured by  $^{31}\text{P}$ -MRS at week 12 depending on randomization group and adjusted for  $^{31}\text{P}$ -MRS at baseline. No additional adjustments/covariates will be used. As this is the single primary outcome, alpha will be set at 0.05. No correction for multiple testing will be performed.

The **secondary analysis** of the primary endpoint will be the comparison of change over time from baseline to week 4, week 8 and week 12, between the DE-group and the DS-group. This will be assessed using a linear mixed model (LME), i.e. NAD ( $^{31}\text{P}$ -MRS) at weeks 4,8 and 12 depending on randomization group, time and their interaction adjusted for random individual intercept.

The **primary analysis** of the secondary endpoint will be performed using ANCOVA between the dose stable (DS-group) and dose escalation group (DS-group), i.e. the regression of NAD or NAD metabolite levels measured by HPLC-MS at week 12 depending on randomization group and adjusted for NAD or NAD metabolite at baseline. No additional adjustments/covariates will be used.

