### **Statistical hypothesis**

Primary analysis:

- Our primary null hypothesis ( $H_0$ ) is that the NR-induced increases in cerebral NAD levels (measured by  $^{31}\text{P}$ -MRS) is not dose-responsive. The alternative hypothesis ( $H_A$ ) is that this increase is dose responsive.

Secondary analysis:

- Mean change between the NR dose escalation arm and NR 1000 mg arm for the dependent variables mentioned above.
- Mean change between and within the NR dose escalation arm, NR 1000 mg arm and placebo arm for the dependent variables mentioned above.

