#### 5.1.2 Primary Inferential Analysis

The *primary analysis* of the *primary endpoint* will be performed using analysis of covariance (ANCOVA) between the dose stable (DS-group) and dose escalation group (DE-group), i.e. the regression of NAD levels measured by P-MRS at week 12 depending on randomization group and adjusted for P-MRS at baseline. No additional adjustments/covariates will be used. As this is the single primary outcome, alpha will be set at 0.05. No correction for multiple testing will be performed.

The formula for this calculation in R is:

```
lm_object = lm(NAD_at_V4 ~ Group + NAD_at_V1)
```

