#### 5.1.3 Effect Estimates

The primary effect estimate will be the B-coefficient with confidence intervals and Cohen's d. Cohen's d will be calculated as the difference in the means between two groups and divided by the pooled standard deviation.

The Beta coefficient will be calculated in R in the following manner:

```
Beta_coffecient = summary(lm_object)$coefficients
```

Confidence intervals will be calculated in R in the following manner:

```
Confidence_intervals = confint(lm_object)
```

P-values will be retrieved from the summary of the lm\_object:

```
P_values = summary(lm_object)$coefficients
```

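### SAP 2.3.3 judges the single primary analysis by a non-inferiority rule with a 15% limit, which does not test the dose-response hypothesis

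*SAP*

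**What the plan says.** SAP 2.3.1 sets a null of no dose response for cerebral NAD measured by 31P-MRS. The alternative "is that NR-induced increase in cerebral NAD levels is dose responsive". It identifies a single primary analysis. Protocol 10.5 matches: the alternative "is that this increase is dose responsive".

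The test is specified in three places. SAP 2.3.2 makes p-values two-sided at 5%: "If a p-value is less than 0.05, the corresponding treatment group difference will be denoted as statistically significant". SAP 5.1.2 gives the model, "lm_object = lm(NAD_at_V4 ~ Group + NAD_at_V1"), comparing DE with DS at alpha 0.05. Protocol 10.4 gives the same comparison: "As this is the single primary outcome, alpha will be set at 0.05". SAP 5.1.3 adds: "The primary effect estimate will be the B-coefficient with confidence intervals".

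SAP 2.3.3, Decision Rule, then says: "Non-inferiority is claimed if the primary null hypothesis is rejected on the significance level (alpha) of 0.025 (one-sided"). It explains this as "if the upper limit of the 95% two-sided confidence interval for the treatment difference is less than 15" per cent.

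SAP 5.5 words the primary hypothesis differently again. Its null covers 31P-MRS NAD or NRRP expression on FDG-PET, and its alternative needs only one of the two to respond to dose. SAP 2.3.1 and Protocol 10.1 name 31P-MRS alone.

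**The concern.** The only section headed Decision Rule attaches a different success criterion to the single primary analysis, and no passage says which criterion prevails. The rule has three faults:

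- It equates two different events. Rejecting a null of no dose response is not the same as an upper confidence limit falling below a positive margin.
- It cannot be applied as written. It does not say whether the difference is DE minus DS or DS minus DE. The margin is a percentage, but the primary estimate is a regression coefficient in NAD/ATP-alpha units. No reason is given for 15%.
- Whichever sign is chosen, meeting it does not show dose response.

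The alpha level is not at fault, because one-sided 0.025 and two-sided 0.05 share the critical value 1.960.

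What is at stake is the trial's one primary conclusion. The SAP is dated 16 June 2025, after the estimated last patient completion of 22.04.2025. Two rules that can disagree leave room to choose between them once results are known. If SAP 5.5 stands, an NRRP result alone could also be read as meeting the primary hypothesis.

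**Working it through.** **1. The two rules on the same data.** Take the difference as DE minus DS, in points of baseline.

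| 95% interval | SAP 2.3.2 / 5.1.2 | SAP 2.3.3 |
|---|---|---|
| +20 to +60 | significant, favours DE | fails (60 > 15) |
| −10 to +10 | not significant | met (10 < 15) |

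With DS minus DE the rules are nested. A significant DE benefit puts the upper limit below 0, hence below 15, so it always meets the rule. The converse is false.

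**2. Inputs for an illustration.**
- Allocation: DE 40, DS 20 (SAP 1.2). A reduced case of 30 vs 15 is also shown.
- Planned effect: SAP 5.5 gives a factor of 1.27 at 1000 mg and linear growth with dose. Reading this as +27% and 3 × 27 = +81%, DE minus DS is 81 − 27 = 54 points.
- Assumption: 15% means 15 points of baseline.
- SD: not given. From the NADPARK NR arm (paired p = 0.016, Protocol 1.3.2), SD = 27 × √n / t. That is 27 × √15 / 2.739 = 38.2 if all 15 were evaluable, or 27 × √10 / 2.958 = 28.9 if 10 were. The placebo arm (−0.43%, p = 0.75, n = 15) gives 0.43 × √15 / 0.325 = 5.1. The SD is therefore open, and 15 to 50 is shown.

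**3. The plan's own figure.** No calculation accompanies the 15% margin. The only sizing figure is 30 in the DE group, which cannot be reproduced without an SD. With 1:2 allocation, 54 points, two-sided 0.05 and 90% power, the normal formula gives n(DS) = (1.960 + 1.282)² × SD² × 1.5 / 54². That is DE 28 at SD 50 and DE 32 at SD 54, so a sizing of 30 corresponds to an SD of roughly 50 to 54. No margin enters it.

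**4. Chance of meeting the 15% rule with no true difference.** SE = SD × √(1/n₁ + 1/n₂) and df = n₁ + n₂ − 3. The probability that estimate + t(0.975, df) × estimated SE falls below 15 is the noncentral-t CDF at −t(0.975, df), with noncentrality (true difference − 15)/SE. For example, at SD 38 with 40 vs 20: SE = 10.41, df = 57, t = 2.002, noncentrality = −15/10.41 = −1.441, probability 0.294. At zero difference the result is the same for either sign.

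| SD | 40 vs 20 | 30 vs 15 |
|---|---|---|
| 15 | 0.948 | 0.871 |
| 20 | 0.768 | 0.640 |
| 27 | 0.514 | 0.404 |
| 38 | 0.294 | 0.230 |
| 50 | 0.189 | 0.151 |

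The two-sided 0.05 test falsely favours DE with probability 0.025. Read as DS minus DE, nesting means that the rule is met without a significant DE benefit in 0.948 − 0.025 = 0.923, 0.294 − 0.025 = 0.269 and 0.189 − 0.025 = 0.164 of trials at SD 15, 38 and 50.

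**5. At the planned effect, read as DE minus DS.** If the true difference equals 15 points the rule is met with probability 0.025 whatever the SD, and less often above that. At +54 points, SD 50 and 40 vs 20, SE = 13.69 and the noncentrality is 39/13.69 = 2.85, giving about 0.000001. The two-sided test then has power 0.972 (0.916 at 30 vs 15). Read as DS minus DE, the rule is met with probability at least 0.9986 at 40 vs 20.

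**The case against.** The strongest reply is that the governing test is clear in practice. SAP 2.3.1, 2.3.2 and 5.1.2 and Protocol 10.4 agree with one another, the protocol has no non-inferiority aim, and the two sentences in 2.3.3 look like unadapted template text. The reference to an infusion in a trial of oral capsules (SAP 3.5) suggests the same. The model and p-value are indeed fully specified, and template origin is plausible. It does not remove the rule, which sits under the heading that defines the decision and is not subordinated to any other passage.

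A second reply is that meeting a non-inferiority margin at zero difference is a correct outcome for a non-inferiority trial. That is true in general. It becomes an error here because 2.3.3 presents the event as rejection of the no-dose-response null. If non-inferiority was really intended, the plan would need its hypothesis, sign, scale, rationale and sample size. With a 15-point margin, no true difference, 90% power and 1:2 allocation, DS would need 29, 64, 103 or 253 patients at SD 20, 30, 38 or 60, against 20 planned.

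Third, the probabilities depend on an assumed SD and on reading 15% as points of baseline. This stands, and they are illustration only.

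Fourth, the NRRP wording is confined to a sample-size section, while SAP 2.3.1, 4.4 and 4.5 treat NRRP as exploratory. It is the lesser inconsistency, but it still contradicts the stated primary hypothesis.

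**Conclusion.** The concern holds and must be fixed. SAP 2.3.3 sets a wrong decision threshold for the single primary analysis, and this follows from the text alone. Under neither sign does meeting the 15% limit show dose response. Under one sign the planned effect fails it, and under the other it can be met without any added effect of escalation.

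The sizes in the working are conditional on 15% meaning points of baseline, full evaluability at 40 vs 20 unless stated, and the assumed SDs. A baseline-adjusted residual SD smaller than the SD of change would raise the no-difference figures.

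**What to change.** Issue one dated SAP revision that states whether treatment was still blinded and whether the database was locked at the time of the change. SAP 2.6 and 3.4.2 give the planned order of these steps, but the available text does not give their status on 16 June 2025.

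1. In SAP 2.3.3, delete the non-inferiority wording and the 15% margin. Replace with: *The primary null hypothesis is rejected if the two-sided p-value for Group (DE vs DS) in the week-12 ANCOVA is below 0.05, i.e. the 95% CI for the DE minus DS coefficient excludes 0; a dose-responsive increase is concluded if the coefficient favours DE.*
2. In SAP 5.5, remove NRRP expression from the null hypothesis and restate the alternative for the single 31P-MRS measure, as in Protocol 10.1 and SAP 2.3.1. The following sentence, which refers to three measures, can be tidied at the same time.

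The cost is a few sentences. Data, model and sample size do not change. SAP 5.1.2 names no reference group (SAP 5.1.7 sets DS as reference only for the mixed model), so the code may need at most one line making DS the reference level, so that the coefficient is DE minus DS.

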## 2.4 Timing of Outcome Assessments

For all clinically planned measures, visits should occur within a window of the scheduled visit. Visits outside visit window is regarded as a protocol deviation. Visits more than 7 days outside the visit window are regarded as a major protocol deviation. The target day and visit window are defined in the protocol as:

Visit Label	Target Day	Definition (Hour window)
Screening	-90 Days	Prior to V1 (Baseline)
V1 (Baseline)	Day 0	Day 0
V2 (Week 4)	Day 28	Target day $\pm$ 72 hours
V3 (Week 8)	Day 56	Target day $\pm$ 72 hours
Last study visit* (Week 12)	Day 84	Target day $\pm$ 72 hours

\*The last study visit is defined as the visit following the last visit with randomised treatment, and where there is a study end statement.

For analysis and tabulation purposes, we define study time points as

Time Point Label	Target Day	Definition (Day window)
V1 (Baseline)	Day 0 (Randomisation)	Information up to randomisation
V2 (Week 4)	28	Days 25 to 31
V3 (Week 8)	56	Days 53 to 59
V4 (Week 12)	84	Days 81 to 87

If more than one visit fall into the same time point interval, information on all visits will be used in the analyses.

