## 2.6 Timing of Main Analysis

The main analysis is planned when all participants have concluded  $84 \pm 7$  days of treatment, all data up to 84 days have been entered, verified and validated and the primary database has been locked.

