### **3.4.2 Protocol Deviations**

The following are pre-defined major protocol deviations regarded to affect the efficacy of the intervention:

- Entering the trial when the eligibility criteria should have prevented trial entry.
- Discontinuation of intervention prior to  $84 \pm 7$  days.
- Major change in concomitant anti-Parkinson medication.
- Received or used other intervention than allocated.
- Adherence to allocated treatment below 85%.
- Visit date interval larger than  $28 \pm 7$  days between individual visits (i.e.: V1 and V2, V2 and V3, and V3 and V4).
- Visit date interval larger than  $84 \pm 7$  days from V1 to V4.
- Not fasting before neuroimaging.

Protocol deviations are classified prior to unblinding of treatment. The number (and percentage) of patients with major and minor protocol deviations will be summarised by treatment group with details of type of deviation provided. The patients that are included in the FAS analysis data set (see point 3.5 below) will be used as the denominator to calculate the percentages. No formal statistical testing will be undertaken.

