#### 5.1.5 Missing Data

For the primary outcome, missing data occur if a patient has not completed the study or not completed P-MRS imaging within the time window of the final visit 12 weeks  $\pm$  7 days.

As the primary analysis uses two timepoints (V1 and V4), in the case of a participant missing V4 measurements, this patient will not be included in the analysis.

For the secondary analysis of the primary outcome using a linear mixed model (LME, see point 5.1.7), missing data will not be imputed but treated as missing at random.

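### SAP 2.4 labels the V4 scan by days 81–87, SAP 4.5 and 5.1.5 accept days 77–91, and no rule says which governs; SAP 5.1.5 also drops V4 scans that were obtained outside days 77–91

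*SAP*

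**What the plan says.** SAP 2.4 has two tables. The first sets visit windows of the target day ± 72 hours, introduced by "The target day and visit window are defined in the protocol as". The second opens with "For analysis and tabulation purposes, we define study time points as" and lists V2 as days 25–31, V3 as days 53–59 and V4 as days 81–87. It is followed by "If more than one visit fall into the same time point interval, information on all visits will be used in the analyses". Any visit outside the window counts as a protocol deviation, and "Visits more than 7 days outside the visit window are regarded as a major protocol deviation".

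Other sections use ±7 days:
- SAP 3.4.2 and Protocol 10.3 list major deviations beginning "Visit date interval larger than", with limits of 28 ± 7 days between consecutive visits and 84 ± 7 days from V1 to V4. These define the per-protocol set (PPS).
- SAP 4.5 gives 84 ± 7 days as the timeframe of the primary endpoint.
- SAP 5.1.5 calls the primary outcome missing if the patient has not completed "imaging within the time window of the final visit 12 weeks" ± 7 days, and says "in the case of a participant missing V4 measurements, this patient will not be included in the analysis".

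Protocol 10.3 defines the intention-to-treat/full analysis set (FAS) as all participants whatever their adherence. Protocol 10.4 puts all randomized patients in the primary analyses and includes a subject with missing assessments where possible. The primary model in SAP 5.1.2 needs one NAD value labelled V4 per patient.

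**The concern.** A V4 scan on day 79 or day 89 is a minor deviation. Under SAP 5.1.5 it is not missing. Under the SAP 2.4 table it belongs to no time point. The statistician must choose, and the choice decides who contributes to the single primary ANCOVA. The SAP is dated 16 June 2025, after the protocol's estimated last-patient date of 22 April 2025, so visit dates may already be known when the choice is made.

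For V2 and V3 there is a gap rather than a conflict. No section states a competing analysis window, but a scan outside days 25–31 or 53–59 has no label for the Visit term in the mixed model of SAP 5.1.7.

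Separately, a V4 scan that exists but lies outside days 77–91 is discarded by SAP 5.1.5. SAP 3.4.2 also removes from the PPS any patient whose V1–V4 interval breaks the same limit. The FAS-versus-PPS comparison in SAP 5.1.6 therefore cannot show what those scans would have done.

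**Working it through.** **Windows for V4, in whole days**
- SAP 2.4 label: 84 ± 3 = 81–87. This reproduces the table (7 days).
- SAP 3.4.2, 4.5 and 5.1.5: 84 ± 7 = 77–91 (15 days).
- SAP 2.4 major-deviation sentence: 7 days beyond the ±72 h window, so 81 − 7 = 74 to 87 + 7 = 94 (21 days).

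Days accepted by 4.5 and 5.1.5 but without a 2.4 label are 77–80 and 88–91, which is 8 of 15. Days that are major deviations under 3.4.2 but not under 2.4 are 74–76 and 92–94. These are day counts, not probabilities.

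**V3.** With V2 on day 28, the 28 ± 7 limit allows V3 on days 49–63. Of these 15 days, 8 (49–52 and 60–63) have no 2.4 label.

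**What FAS versus PPS can still test.** Visits on days 28, 50 and 88 give V2–V3 = 22 days and V3–V4 = 38 days. The patient leaves the PPS (38 > 35) but has a V4 scan inside 77–91, so stays in the FAS analysis under 5.1.5. Between-visit spacing is therefore tested; scans outside 77–91 are not.

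**Size.** No visit dates or spread are given, so both are assumed: V4 day is normal with SD 2, 3 or 4 and is rounded to whole days. Two centres are used because the documents support both. Day 84 follows from weeks 4, 8 and 12. Day 90 follows from Protocol 3.1 (visits 30 days apart, 90 days in total), which would put V3 on day 60 and V4 on day 90, both outside the 2.4 ranges.

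With centre m:
- P(81–87) = Φ((87.5 − m)/SD) − Φ((80.5 − m)/SD)
- P(77–91) = Φ((91.5 − m)/SD) − Φ((76.5 − m)/SD)
- disputed share = P(77–91) − P(81–87)
- share dropped by 5.1.5: f = 1 − P(77–91)
- SE factor for the DE–DS difference, with equal loss in both arms: 1/√(1 − f)

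| Centre | SD | In 81–87 | In 77–91 | Disputed | Of 60 (DE + DS) | Dropped by 5.1.5 | SE factor from 5.1.5 |
|---|---|---|---|---|---|---|---|
| 84 | 2 | 92.0% | 99.98% | 8% | 5 | 0.02% | 1.000 |
| 84 | 3 | 75.7% | 98.8% | 23% | 14 | 1.2% | 1.006 |
| 84 | 4 | 61.8% | 93.9% | 32% | 19 | 6.1% | 1.032 |
| 90 | 2 | 10.6% | 77.3% | 67% | 40 | 23% | 1.137 |
| 90 | 3 | 20.2% | 69.1% | 49% | 29 | 31% | 1.203 |
| 90 | 4 | 25.7% | 64.6% | 39% | 23 | 35% | 1.244 |

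Differences were taken before rounding.

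If the 2.4 ranges were used to decide inclusion, which the SAP does not say, the SE relative to the ±7 rule would be √(P(77–91)/P(81–87)). At centre 84 this is 1.043, 1.142 and 1.232, a rise of 4%, 14% and 23%. At centre 90 it would be larger.

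**The case against.** The strongest reply is that SAP 5.1.5 is the only rule that excludes anyone from the primary ANCOVA. It is specific to the endpoint and SAP 4.5 agrees with it. A specific missing-data rule would naturally override a general label table, which leaves a drafting slip. That reading is sensible and probably intended, but the SAP does not state it. The 2.4 table cannot be set aside as scheduling only: scheduling has its own table directly above, and the sentence after the second table ties its intervals to the analyses.

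A ±3-day target with a wider limit for major deviations is also an ordinary tiered scheme, and the 3.4.2 limits serve the PPS. This stands. The direct conflict over the V4 value is between 2.4 and 4.5/5.1.5. Section 3.4.2 conflicts directly only with the major-deviation sentence in 2.4.

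A timing window for a week-12 endpoint is a legitimate choice, and Protocol 10.4 softens its wording and refers to the SAP for detail. That also stands in part. However, an obtained late scan is one that can be included, so discarding it departs from the protocol's wording.

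A reader might infer that SAP 2.4 deletes scans outside days 81–87. It states no such rule. A reader might also infer freedom to choose the PPS after seeing results. SAP 3.4.2 requires deviations to be classified before unblinding, which limits that, although it does not cover the assignment of 2.4 labels.

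**Conclusion.** The inconsistency is real and should be settled before unblinding. Two sections define V4 differently for the same primary analysis, and 8 of the 15 accepted days are in dispute. Two major-deviation limits also disagree (74–94 against 77–91). In addition, SAP 5.1.5 discards obtained scans that the protocol's analysis-set wording would keep, and the planned sensitivity analysis cannot examine them.

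The size rests entirely on assumed visit days. Centred on day 84, the disputed share is 8–32% and the loss from the ±7 limit is small, at most about 6%. Centred on day 90, the disputed share is 39–67% and the ±7 limit itself drops about 23–35%, raising the SE by 14–24%. It is therefore not safe to call the ±7 loss negligible without the visit dates.

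It would be tempting to conclude that the DE–DS estimate is biased. The documents do not support that: the windows apply equally to all arms, and nothing shows that timing differs by arm. The number of scans actually affected is unknown.

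**What to change.** In the SAP:
1. Assign scans by nominal visit (V1–V4) in the FAS. Delete the 2.4 day-range table or align it to the ±7-day limits.
2. Keep every obtained V4 scan in the primary ANCOVA. Use 28 ± 7 and 84 ± 7 only to define the PPS.
3. Record whether the participant was still on the allocated dose at the V4 scan, using the medication end date that SAP 3.4.1 already needs for compliance. Report a sensitivity analysis without V4 scans taken after study drug had stopped.
4. Replace the 2.4 major-deviation sentence with the 3.4.2 limits.
5. Minor wording: SAP 2.6 waits for 84 ± 7 days of treatment but asks only that "all data up to 84 days have been entered, verified and validated"; change this to data up to and including V4. Correct the statement that the ±72 h visit window comes from the protocol. In the protocol text available, the only 72-hour rule concerns imaging relative to the physical examination (Appendix B).

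The cost is wording only, with no new data. The downside is slightly more spread in scan timing and a few late scans that may be off 3000 mg. Therapy is planned for 12 weeks and dispensing is scheduled at V1–V3, although the study nurse can resupply. Item 3 addresses this.
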